### 5.3.2 Secondary Safety Endpoint

1. The proportion of subjects reporting one or more device- or procedure-related SAEs, as assessed at 30 days, 75 days, 90 days, 6 months and 12 months of follow-up.
2. The proportion of subjects with stroke or TIA through 12 months
3. The proportion of subjects with major bleeding related to anticoagulation treatment through 12 months
4. The proportion of subjects requiring cardioversion through 12 months
5. The proportion of subjects requiring an arrhythmia-related hospitalization through 12 months

### 5.3.3 Primary Feasibility Endpoint

The proportion of subjects that achieve Acute Procedural Success (APS) defined as the percutaneous endocardial creation of a complete, electrically isolating set of lesions around the ostia of the pulmonary veins (PVI) using the FARAPULSE Endocardial Ablation System during the first procedure, as clinically assessed by entrance and/or exit block performed  $\geq$  20 minutes after the last PVI lesion is made.

### 5.3.4 Secondary Feasibility Endpoint

1. The proportion of subjects that achieve Chronic Procedural Success (CPS) defined as persistent electrical isolation of all initially ablated pulmonary veins assessed during an electroanatomical mapping procedure performed 75 days following the index procedure. Chronic Procedural Success will be subdivided by single procedure and reablated subjects.
2. The proportion of subjects that achieve Therapeutic Success, defined as freedom from:
  - a. Post blanking period through assessment: occurrence of AF, AFL or AT, or ablation for AF/AFL/AT using the study device
  - b. At any time: ablation for AF/AFL/AT with a nonstudy device

Therapeutic success will be assessed from the end of the blanking period at Months 6 and 12, and will be subdivided by on / off AFDs post blanking period.

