PLANNED PROCEDURE:	Subjects will undergo an attempt to isolate all 4 pulmonary veins or their anatomic equivalent. Subject with a past history of or having inducible isthmus-mediated flutter will undergo interruption of the cavo-tricuspid isthmus at the discretion of the investigator. Additional lesions may be made at the discretion of the investigator.
PRIMARY SAFETY ENDPOINT:	
The primary safety endpoint for this study is the Composite Safety Endpoint (CSE) defined as the incidence of the following early-onset and late-onset serious adverse events (SAEs) which are device- or procedure-related:
 
Early onset (within 30 days of any endocardial ablation for atrial fibrillation)
 

• Death

• Myocardial infarction (MI)

• Persistent diaphragmatic paralysis

• Stroke or transient ischemic attack (TIA)

• Peripheral or organ thromboembolism

• Pericarditis

• Cardiac tamponade / perforation

• Vascular access complications

• Hospitalization (initial or prolonged)*

• Heart block

 
Late onset (any time during follow-up)
 

• Pulmonary vein (PV) stenosis (> 70% diameter reduction from baseline)

• Atrio-esophageal fistula

 
* Excludes hospitalization (initial & prolonged) solely due to arrhythmia (AF/Atrial Flutter/Atrial Tachycardia) recurrence or due to non-urgent cardioversion (pharmacological or electrical). Hospitalization excludes visits to hospital-associated outpatient facilities such as clinics or emergency wards.

**SECONDARY  
SAFETY  
ENDPOINT:**

1. The proportion of subjects reporting one or more device- or procedure-related SAEs, as assessed at 30 days, 75 days, 6 months and 12 months of follow-up.
2. The proportion of subjects with stroke or TIA through 12 months
3. The proportion of subjects with major bleeding related to anticoagulation treatment through 12 months
4. The proportion of subjects requiring cardioversion through 12 months
5. The proportion of subjects requiring an arrhythmia-related hospitalization through 12 months

**PRIMARY  
FEASIBILITY  
ENDPOINT:**

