### **4.2 Intended Use**

The FARAPULSE Endocardial Ablation System is indicated for cardiac tissue ablation for the treatment of paroxysmal atrial fibrillation.

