**Table 2: Components and Model Numbers of the FARAPULSE Endocardial Ablation System**

System Components	System Model Number (REF#)
FARAWAVE Endocardial Ablation Catheter System  1. Ablation Catheter (31 mm or 35 mm) 2. Extension Cable	40T401 and 40T404
FARASTAR Endocardial Generator System  1. Pulsed Electric Field Generator (PEFG) 2. Two Coaxial Cables 3. Two Pace Filter Boxes 4. Two Catheter Switch Boxes	60T401
FARADRIVE Deflectable Sheath System (or commercially available CE Marked Deflectable Sheath System such as the CE Marked Oscar Destino™ Twist UniDirectional Deflectable Guiding Sheath)*  1. Sheath 2. Dilator	20T401

CE Marked Devices That May be Used in Conjunction with FARAPULSE Endocardial Ablation System
*Oscor Destino™ Twist UniDirectional Deflectable Guiding Sheath
St. Jude BRK 98cm Transseptal Needle
MicroPace StimCor Cardiac Stimulator

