#### 4.4.1 FARAWAVE Endocardial Ablation Catheter System

[figure not shown]
The FARAWAVE Endocardial Ablation Catheter System consists of two (2) components: Ablation Catheter and Extension Cable, which are used together. Both components are sterile and single use only.

The ablation catheter is offered in two different sizes: 31 mm (REF 40T401) and 35mm (REF 40T404) deployed diameters, to accommodate varying pulmonary vein anatomy. Selection of either catheter will be at the investigator's discretion.

The Ablation Catheter is a multi-electrode catheter that connects electrically to the Endocardial Generator System. It consists of a multi-electrode ablation catheter with electrodes arranged on splines. The Ablation Catheter consists of a distal section with five splines that deploy into a flower-shaped configuration with five petals, a shaft section, and a proximal handle with a manually operated deployment control (Figure 2). Each petal has a single electrode that is separately wired to facilitate connection to a mapping or recording system (this is an optional feature offered to the user). The handle includes a flush port for saline infusion, a deployment control knob with a guidewire lumen hub that can be connected to a hemostasis valve, and a cable with connectors. The catheter connectors connect to an Extension cable (also part of the Endocardial Ablation

Catheter System) with numbered connectors on each of its ends. These connect to the multi-channel Endocardial Generator. The Pulsed Electric Field energy is delivered via the PEF Generator over the set of ablation catheter electrodes. The Extension Cable is a single-use sterile cable that provides additional cable length to connect to the Endocardial Generator.

Additional details are provided in the IFU LBL0195 for the specific use and procedural steps of the Endocardial Ablation Catheter System.

**Figure 2: Representative Illustration of Deployed Endocardial Ablation Catheter with Fully Deployed Distal “flower” Section.  
Provided in 31mm and 35mm Deployed Diameters**

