#### **4.4.2 FARASTAR Endocardial Generator System**

The FARASTAR Endocardial Generator System consists of the following components – Pulsed Electric Field Generator (PEFG), BNC Coaxial Cable (2 units), Pace Filter Box (2 units), and Switch Box (2 units). The Endocardial Generator System is designed to deliver Pulsed Electric Field (PEF) energy to endocardial sites in the heart via the Endocardial Ablation Catheter System and other compatible devices (refer to IFU LBL0195 for the specific use and procedural steps of the Endocardial Ablation Catheter System, LBL0193 for the Deflectable Sheath System and LBL0198 for the Endocardial Generator System).

The Pulsed Electric Field Generator is a 16-channel output unit that generates a pulsed voltage waveform that can be delivered to the ablation catheter electrodes. The FARASTAR Generator, while capable of operating between 1400V and 2100V, currently allows ablation energy in discrete user-selectable voltage settings between 1400V and 2000V.

As an input, a compatible cardiac stimulator unit for cardiac pacing is applied to the cardiac chambers via pacing catheters and to the PEFG with a coaxial cable to synchronize the application of therapeutic PEF energy to the actively paced heart. The physician confirms proper synchronization by actuating a button on the

PEFG user interface. The BNC Coaxial Cable is used to connect the generator to a commercially available compatible cardiac stimulator/pacing device.

Details regarding the generator are provided in the FARASTAR Endocardial Generator System User Manual LBL0198.

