### **5.2.2 Exclusion Criteria**

Subjects will be excluded from participating in this study if they meet any one of the following exclusion criteria:

1. Use of amiodarone within 3 months prior to enrollment
2. Atrial fibrillation that is any of the following
  - a. Persistent (by diagnosis or duration  $> 7$  days)
  - b. Secondary to electrolyte imbalance, thyroid disease, alcohol abuse or other reversible / non-cardiac causes
  - c. Requires  $\geq 3$  cardioversions in the preceding 12 months
3. Cardiac anatomical exclusions by imaging within 3 months prior to enrollment:
  - a. Left atrial anteroposterior diameter  $\geq 5.0$  cm as documented by transthoracic echocardiography (TTE) or computed tomography (CT)
  - b. Left ventricular ejection fraction  $\leq 40\%$  as documented by TTE
4. Any of the following cardiac procedures, implants or conditions:
  - a. Clinically significant arrhythmias other than AF
  - b. Hemodynamically significant valvular disease
  - c. Prosthetic heart valve
  - d. NYHA Class III or IV CHF
  - e. Previous endocardial or epicardial ablation or surgery for AF
  - f. Atrial or ventricular septal defect closure
  - g. Atrial myxoma
  - h. Left atrial appendage device or occlusion
  - i. Pacemaker, ICD or CRT
  - j. Significant or symptomatic hypotension
  - k. Bradycardia or chronotropic incompetence
  - l. History of pericarditis
  - m. History of rheumatic fever
5. Any of the following within 3 months of enrollment:
  - a. Myocardial infarction
  - b. Unstable angina

- c. Percutaneous coronary intervention
- d. Heart surgery (e.g. coronary artery bypass grafting, ventriculotomy, atriotomy)
- e. Heart failure hospitalization
- f. Stroke or TIA
- g. Clinically significant bleeding
- h. Pericarditis or pericardial effusion
- i. Left atrial thrombus

6. History of blood clotting or bleeding abnormalities.
7. Contraindication to, or unwillingness to use, systemic anticoagulation
8. Contraindications to CT or MRI
9. Sensitivity to contrast media not controlled by premedication
10. Women of childbearing potential who are pregnant, lactating or not using birth control
11. Serious or untreated medical conditions that would prevent participation in the study, interfere with assessment or therapy, or confound data or its interpretation, including but not limited to
  - a. Solid organ or hematologic transplant, or currently being evaluated for an organ transplant

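### Read literally, Therapeutic Success criterion (b) fails a subject from day 0 for a planned index isthmus line made with a nonstudy catheter

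*Combined protocol and SAP*

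**What the plan says.** Therapeutic Success is the second secondary feasibility endpoint and has two failure criteria.

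- Criterion (a): "Post blanking period through assessment: occurrence of AF, AFL or AT, or ablation for AF/AFL/AT using the study device".
- Criterion (b): "At any time: ablation for AF/AFL/AT with a nonstudy device".

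The wording is the same in Section 5.3.4, Section 7.5.2 and the Executive Summary. Success is assessed at Months 6 and 12.

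Under Planned Procedure, the Executive Summary covers a subject with earlier isthmus-mediated flutter, or "having inducible isthmus-mediated flutter will undergo interruption of the cavo-tricuspid isthmus at the discretion of the investigator". It also permits further lesions at the investigator's discretion. It names no device for either.

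Section 5.2.2, item 4a, excludes "Clinically significant arrhythmias other than AF". Section 7.1 states that the study is descriptive, with no formal hypothesis test.

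**The concern.** Isthmus-mediated flutter is AFL, so an isthmus line is an ablation for AFL. Criterion (b) has no start date and no index-procedure exception. A subject who receives the line as planned, from a nonstudy catheter, has therefore failed before follow-up begins. If the investigator makes the same line with the study catheter, neither criterion is met: (b) does not apply to the study device, and (a) has not yet started.

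If such lines are made, part of the reported Therapeutic Success rate reflects which catheter was used for a right-sided line at index, not whether arrhythmia recurred. The error runs in one direction only, and enrolling more subjects does not shrink it. Section 7.2 says the data will inform the powering of a later pilot study, so the rate has a use beyond this report.

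**Working it through.** The plan gives no expected Therapeutic Success rate and no count of isthmus lines, so there is no figure of its own to reproduce. The check has two parts.

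**Would a nonstudy catheter be used?** The text leaves this open.

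- Pointing towards nonstudy use: the study catheter comes in two sizes "to accommodate varying pulmonary vein anatomy" (Section 4.4.1). The system is "indicated for cardiac tissue ablation for the treatment of paroxysmal atrial fibrillation" (Section 4.2), with no mention of flutter. Section 5.12.2 describes vein-by-vein ablation and has no isthmus step. Section 6.2 describes energy delivery in the pulmonary veins.
- Pointing away: the Table 2 list headed "CE Marked Devices That May be Used in Conjunction with FARAPULSE Endocardial Ablation System" contains no ablation catheter. It is not exhaustive, however, since it also omits the commercial pacing and diagnostic catheters that Section 5.12.2 requires. Section 4.4.2 says the generator can deliver "energy to endocardial sites in the heart via the Endocardial Ablation Catheter System and other compatible devices", so a study-system isthmus line is not ruled out.
- Limiting the number: exclusion 4a removes subjects with clinically significant flutter at screening. It does not remove flutter first induced at the procedure, or past flutter judged not clinically significant.

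**How large could the effect be?** Inputs: N = 80 (the maximum in Section 5.4) and an assumed 60/80 successes (75%) if index isthmus lines are not counted. Let k be the number of subjects with a nonstudy index isthmus line, and s ≤ k the number of those who would otherwise have succeeded.

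Rate under (b) as written = (60 − s)/80, so each such subject costs 1/80 = 1.25 percentage points. Affected subjects who would have failed anyway change nothing.

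- k = 1: from 59/80 = 73.75% to 75.0%
- k = 2: from 58/80 = 72.5% to 75.0%
- k = 4: from 56/80 = 70.0% to 75.0%

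To compare with sampling error, take the exact (Clopper-Pearson) 95% interval and find the smallest s that moves the rate below its lower limit:

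| Assumed successes | Rate | Exact 95% CI | Smallest s |
|---|---|---|---|
| 48/80 | 60% | 48.4–70.8% | 10 |
| 56/80 | 70% | 58.7–79.7% | 10 |
| 60/80 | 75% | 64.1–84.0% | 9 |
| 64/80 | 80% | 69.6–88.1% | 9 |
| 68/80 | 85% | 75.3–92.0% | 8 |

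For 60/80: s = 8 gives 52/80 = 65.0%, above 64.1%; s = 9 gives 51/80 = 63.75%, below it.

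**The case against.** The strongest reply is that (b) is a clear and deliberate rule. The objective concerns treatment with this system. Section 7.1 assesses device performance by vein isolation with the study device alone. Section 5.12.5 scores nonstudy gap closure at the remapping visit as a therapeutic failure, and that visit falls at 75 ± 15 days (days 60 to 90), within the 90-day blanking period. The different start times of (a) and (b) therefore look chosen.

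Much of this stands. A reader might infer that the plan leaves the scoring of an isthmus line undefined. It does not: *at any time* settles it, and the issue is what the strict rule captures. But the study-device language in Sections 7.1 and 5.12.5 concerns pulmonary veins. Nonstudy gap closure in a vein says something about the study device's lesions; a planned right-sided line for a different arrhythmia does not. No section says (b) was meant to reach that line.

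The second reply is that several things must coincide: an eligible subject with past or inducible isthmus flutter, an investigator who decides to make the line, a nonstudy catheter, and an otherwise successful outcome. That is correct, and it keeps the point minor. A third reply is that Section 7.1 already allows other secondary analyses. It does, but it does not specify this one, and a scoring choice is more credible when fixed before outcomes are known.

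**Conclusion.** The point holds as a conditional one of minor weight. As written, (b) would score a planned index lesion as failure from day 0 when a nonstudy catheter makes it, and would ignore the same lesion when the study device makes it.

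The size is 1.25 points per affected would-be success if 80 subjects are analysed. Section 7.4 uses available data only, so with n evaluable subjects the figure is 1/n. Under the assumed rates of 60% to 85%, 8 to 10 such subjects would be needed to move the rate outside its own interval. The likely effect is smaller than sampling error.

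A reader might go further and infer that nonstudy isthmus lines will be common and the rate badly understated. The documents do not support that. They state no count and no device, exclusion 4a points to few cases, and the number may be zero. Nor is any primary conclusion at risk: Acute Procedural Success, Chronic Procedural Success and both additional endpoints concern pulmonary veins only.

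**What to change.** Keep (b) unchanged as the main definition. Prespecify a second version, reported beside it at Months 6 and 12, in which (b) reads: *nonstudy-device ablation of AF, AFL or AT at any time, except cavo-tricuspid isthmus ablation for isthmus-mediated flutter performed during the index procedure*. Every other nonstudy ablation stays a failure in both versions, including additional index lesions for AF, later isthmus ablation and day-75 gap closure. Report the number of index isthmus lines by device, study or nonstudy. If no nonstudy line was made, the two versions agree and one sentence says so.

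The cost is one extra table row and one count. The procedural data list in Section 5.12.2 has no item for isthmus lesions or nonstudy ablation catheters. Section 11.2.1 requires the device used to be documented in the medical record but does not mention lesion site. One case report form field or a short chart review may therefore be needed, including for the 16 subjects that Section 3.4.1 reports as already enrolled. The excepted version is slightly less attributable to the study device alone and is added after enrolment began; showing both versions makes the effect of each visible.

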### **5.3.5 Additional Endpoints**

1. Proportion of all ablated pulmonary veins that are isolated at the index procedure using the study device.
2. Proportion of all ablated pulmonary veins acutely isolated using the study device that remain isolated at the 75 day remapping procedure.

### **5.4 Sample Size**

Up to 80 subjects will be enrolled in this clinical safety and feasibility study.

### **5.5 Investigational Sites**

The clinical study will be conducted at Nemocnice Na Homolce in Prague, Czech Republic and at Hopital cardiologique du Haut-Leveque, Pessac, France.

### **5.6 Duration of Subject Participation**

Subjects will be followed at 7 days, 30 days, 75 days, 90 days, 6 months and 12 months with a blanking period for recurrent atrial fibrillation or atrial tachycardia of 90 days following the index PEF catheter ablation procedure.

The enrollment period is estimated to take 9 months and subjects will be followed for up to 12 months for a total duration of approximately 21 months.

### **5.7 Written Informed Consent**

All subjects must provide written Informed Consent using the Ethics Committee approved Informed Consent Form before undergoing any study related procedures. Subjects cannot be asked to sign the Informed Consent document until the study has been fully approved by the institution's EC and by the Competent Authority, if applicable, and the Sponsor or their CRO representative has received and reviewed the EC-approved Informed Consent Form. Subjects who meet the general entry criteria will be asked to sign a Patient Informed Consent form as approved by the relevant regulatory authorities before any study-specific tests or procedures are performed. The Investigator or a designated member of his/ her staff should approach the subject to obtain written informed consent. As far as possible, non-technical language shall be used that is understandable to the subject. The background of the proposed study and the benefits and risks of the procedures and study should be explained. The subject should be provided with ample time to read the consent form and discuss it with their family and physician. The subject shall be informed that his/ her participation in the clinical investigation is confidential. The Informed Consent Form must be read and understood by the subject and the subject's questions answered. The form must be signed and dated by both the subject and Investigator conducting informed consent prior to subject enrollment and before the subject undergoes any study related procedures. All subjects are to receive copies of their signed and dated Informed Consent Form. A copy of the approved Informed Consent Form along with a copy of each patient's signed consent form will be maintained by the Investigator in a designated clinical study

administrative file. Subjects may not be consented after receiving any medication that might alter their ability to comprehend the consent form (e.g. sedatives, narcotics, etc.). Study personnel should explain that even if a subject agrees to participate in the study and signs the Patient Informed Consent Form, the subject may not be eligible to participate if he/ she fails to meet the screening criteria.

Written informed consent must be obtained prior to performing any protocol driven tests or any procedures that are not standard of care for a percutaneous ablation procedure that the subject is scheduled to undergo.

Once written consent has been obtained, the subject will be entered on a Screening Log, which will be maintained at the site.

#### **5.8 Enrollment**

Subjects that meet all of the eligibility criteria and are deemed suitable by the investigator will be invited to participate in the study.

Subjects will be considered enrolled at the time of signing the Informed Consent Form.

Each subject will be assigned a unique study identification code to protect each subject's confidential health information. The unique study identification code will not include date of birth or subject's first and last initials and will be used to link study data and other study information to the subject in lieu of the subject name. The Subject Name Log will be used to link the unique study identity code to the subject and will be maintained at the site. This log will remain confidential and will not be provided to the Sponsor, but only used for reference when monitoring at the study site.

#### **5.9 Withdrawal of Subjects**

Subjects may voluntarily withdraw from the study at any time for any reason. In addition, the investigator may withdraw the subject due to any of the following situations:

- adverse event (AE); or
- study investigator may withdraw a patient from the study without the patient's consent if the investigator has a concern for the patient's rights, safety or welfare

Subjects with an ongoing AE at the time of withdrawal should be followed on study until the clinical event has been resolved or is stable if possible.

